6.1.2.2.2 Partial Response (PR)/Stable Disease (SD)

The persistence of one or more nontarget lesion(s).

6.1.2.2.3 Progressive Disease (PD)

The appearance of one or more new lesion(s) and / or unequivocal progression of existing non target lesions.

6.1.2.3 Symptomatic Deterioration

Patients with a global deterioration of health status requiring discontinuation of treatment without objective evidence of disease progression at that time should be classified as having *symptomatic deterioration*.

6.1.3 Evaluation of Patient's Best Overall Response

The best overall response is the best response recorded from registration until disease progression/recurrence, taking as reference for progressive disease the smallest measurements recorded since registration. Table 9 below provides overall responses for all possible combinations of tumor responses in target and nontarget lesions, with or without new lesions.

To be assigned a status of stable disease, measurements must have met the stable disease criteria at least once after study entry at a minimum interval of eight weeks.

Table 9. Overall Response for all Possible Combinations of Tumor Response

Target Lesions	Nontarget Lesions	New Lesions	Overall Response
CR	CR	No	CR
CR	Incomplete response/SD	No	PR
PR	Non-PD	No	PR
SD	Non-PD	No	SD
PD	Any	Yes or No	PD
Any	PD	Yes or No	PD
Any	Any	Yes	PD

CR = complete response; PR = partial response; SD = stable disease; PD = progressive disease

NOTE: BOTH CLINICAL (by ENT examination) AND RADIOGRAPHIC RESPONSE (by CT or MRI scan) will be recorded. Response in the primary and the neck will be reported separately.

6.1.3.1 First Documentation of Response

The time between initiation of therapy and first documentation of PR or CR.

6.1.3.2 Confirmation of Response

To be assigned a status of complete or partial response, changes in tumor measurements must be confirmed by repeat assessments performed no less than four weeks after the criteria for response are first met.

6.1.3.3 Duration of Response

Duration of overall response - the period measured from the time that measurement criteria are met for complete or partial response (whichever status is recorded first) until the first date that recurrent or progressive disease is objectively documented, taking as reference the smallest measurements recorded since treatment started.

6.1.3.4 Duration of Overall Complete Response

The period measured from the time measurement criteria are met for complete response until the first date that recurrent disease is objectively documented.

6.1.3.5 Duration of Stable Disease

A measurement from registration until the criteria for disease progression is met, taking as reference the smallest measurements recorded since registration. To be assigned a status of stable disease, measurements must have met the stable disease criteria at least once after study entry at a minimum interval of six weeks.

6.1.3.6 Survival

Survival will be measured from the date of entry on study.

6.1.3.7 Time to Progression and Progression-free survival

This interval will be measured from the date of entry on the study to the appearance of new metastatic lesions or objective tumor progression. Progression-free survival (PFS) will be calculated from treatment initiation to disease progression or death from any cause or last follow up.

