4. PATIENT REGISTRATION/RANDOMIZATION

Note: All patients can be registered following eligibility confirmation by calling the coordinating center study liaison, [name], BSN:

[name]
 [name]
 [name]
 [contact]
 [contact]
 E-mail: [contact]

For questions regarding the eligibility of subjects, please contact the study doctor, [name], at [contact].

Registration will require the following information: 1) your name, telephone and email; 2) protocol name and number; 3) date treatment begins; 4) subject name; 5) date of birth; 6) subject hospital medical record number; 7) primary study physician; 8) primary treatment institution; 9) confirmation of eligibility; 10) copies of the informed consent signature page and 11) verification that the informed consent was signed.

Randomization will occur at the UPCI Biostatistics Core once consent and eligibility are verified.

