5. TREATMENT PLAN

Arm 1 (Table 2): Pembrolizumab will be initiated 2 weeks after the completion of cisplatin-IMRT (week 9 of protocol treatment) and administered at the fixed dose of 200 mg IV q 3 weeks (+/- 3 days) for a total of 24 weeks (8 doses; 6 months). NOTE: Per discretion of the treating investigator, the week 9 dose of pembrolizumab may be delayed up to 3 weeks for recovery of acute toxicities from chemoradiotherapy. This dose would be considered delayed, and all subsequent doses would be administered at a q 3 week interval (+/- 3 days) from first pembrolizumab dose.

Arm 2 (Table 3): Pembrolizumab will be initiated 1 week prior to cisplatin-IMRT (the “window”) at the dose of 200 mg IV q 3 weeks (+/- 3 days). Pembrolizumab will be continued concurrently through cisplatin-IMRT (weeks 3, 6), and continued for a 15 week maintenance period after completion of cisplatin-IMRT for a total pembrolizumab treatment period of 24 weeks (8 doses; 6 months). NOTE: Per discretion of the treating investigator, the week 9 dose of pembrolizumab may be delayed up to 3 weeks for recovery of acute toxicities from chemoradiotherapy. This dose would be considered delayed, and all subsequent doses would be administered at a q 3 week interval (+/- 3 days) until completion.

Table 2. Arm 1 Treatment Plan

ARM 1	Week of Treatment														
	1	2	3	4	5	6	7	9	12	15	18	21	24	25	30
IMRT	X	X	X	X	X	X	X								
Cisplatin	X	X	X	X	X	X	X								
Pembrolizumab								X	X	X	X	X	X	X	X

Table 3. Arm 2 Treatment Plan

ARM 2	Week of Treatment													
	-1	1	2	3	4	5	6	7	9	12	15	18	21	
IMRT		X	X	X	X	X	X	X						
Cisplatin		X	X	X	X	X	X	X						
Pembrolizumab	X			X			X		X	X	X	X	X	

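### PFS is timed from first treatment while survival and time to progression run from study entry, so the trial's gating and selection metric has a post-randomization start that differs by arm relative to radiotherapy

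*Combined protocol and SAP*

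**What the plan says.** Section 6.1.3.7 covers two endpoints and gives them different origins. For time to progression it says "This interval will be measured from the date of entry on the study to the appearance of new metastatic lesions or objective tumor progression". For PFS it says "Progression-free survival (PFS) will be calculated from treatment initiation to disease progression or death from any cause or last follow up". Section 6.1.3.6 adds, "Survival will be measured from the date of entry on study". Section 6.1.3.5 uses a third label for the duration of stable disease: "A measurement from registration until the criteria for disease progression is met". Study entry is nowhere tied to registration or to randomization.

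On the order of events, Section 4 says "Randomization will occur at the UPCI Biostatistics Core once consent and eligibility are verified", so randomization comes before any treatment. In Section 5, Arm 1 begins with cisplatin-IMRT in week 1. For Arm 2, "Pembrolizumab will be initiated 1 week prior to cisplatin-IMRT".

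Section 9 (Sample Size Determination) uses 1-year PFS twice: as one of three criteria that an arm must meet to advance, and, if both arms meet them, as the figure that picks the winner by numerical superiority. It gives no other start date for PFS. It plans 40 evaluable patients per arm, allows 10% for drop-out or ineligibility, randomizes 90, and analyzes the evaluable patients. Evaluable is not defined for efficacy.

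**The concern.** In a randomized trial the natural origin for a time-to-event endpoint is randomization, because up to that moment the arms differ only by chance. A clock that starts at first treatment starts after assignment is known, and this trial is open-label.

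Three things follow from the text:

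- Arm 2's PFS year begins a week before radiotherapy and Arm 1's begins with it.
- PFS and survival for the same arm have different origins and, potentially, different risk sets.
- A patient who progresses or dies after randomization but before treatment can be counted in survival but cannot be placed on the PFS curve.

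With about 40 patients per arm and selection on any numerical difference, the definition of the metric should be beyond dispute before outcomes are seen.

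**Working it through.** **Plan's own figure.** 40 evaluable per arm with a 10% allowance gives 40 / 0.9 = 44.4, rounded up to 45 per arm, or 90 in total. This matches Section 9, and no change of time zero alters it.

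**1. The arm offset.** Inputs: the one-week lead-in (Section 5), the 60% reference for 1-year PFS (Section 9) and n = 40. Assumptions, most favorable to finding a bias: exponential PFS from the start of IMRT, equal efficacy, IMRT starting equally soon after randomization in both arms, and no events in Arm 2's lead-in week. Arm 2's year then covers 51 weeks from IMRT and Arm 1's covers 52, so Arm 2's 1-year PFS is S^(51/52).

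| Underlying 1-year PFS, S | Arm 2, S^(51/52) | Difference, points | Patients in 40 | Arm 2 ahead / Arm 1 ahead / tie | Arm 2 picked, ties split |
|---|---|---|---|---|---|
| 60% | 60.6% | 0.6 | 0.24 | 47.6% / 43.3% / 9.1% | 52.2% |
| 70% | 70.5% | 0.5 | 0.19 | 47.0% / 43.3% / 9.7% | 51.9% |
| 75% | 75.4% | 0.4 | 0.17 | 46.6% / 43.1% / 10.3% | 51.7% |

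For scale, the standard error of the difference between arms at 70% is sqrt(2 × 0.7 × 0.3 / 40) = 0.102, or about 10 points.

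If the hazard in the lead-in week equals the hazard afterwards, both arms have S(52) from their own start and the offset has no effect.

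**2. The gap between randomization and treatment.** Under a constant hazard, the 1-year PFS of patients who reach treatment event-free after w weeks is S(52 + w) / S(w) = S(52). At the reference rate and w = 4, that is 0.5769 / 0.9615 = 0.600, the same as from randomization. If instead no events occur in the gap, PFS at one year from randomization is S(52 − w). For w = 2 that is 0.612, so the treatment clock gives the lower figure. The gap therefore has no fixed sign or size.

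**3. Randomized but untreated patients at the gate.** Section 9 accepts an arm on PFS if the lower one-sided 90% exact bound exceeds 0.60. The bound for x of n is the 10% quantile of a Beta(x, n − x + 1) distribution.

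| Progression-free / n | Lower bound | Gate |
|---|---|---|
| 28/40 | 0.588 | fails |
| 29/40 | 0.615 | passes |
| 29/41 | 0.598 | fails |
| 29/42 | 0.582 | fails |
| 29/45 | 0.538 | fails |

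With 40 patients the gate needs at least 29 successes, and the chance of reaching that at a true 60% is 0.071. The one-week offset would raise it to 0.082 in Arm 2 under the assumptions in step 1.

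At the threshold, one untreated patient counted as a failure reverses the result. Section 9 also states the criterion as an observed PFS of at least 60%. On that reading the same holds at its own threshold: 24/40 = 60.0% passes and 24/41 = 58.5% does not.

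**The case against.** The strongest reply is that this is a labeling inconsistency of little numerical consequence, and much of that stands.

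- **The offset needs special assumptions.** It depends on an event-free lead-in week and on IMRT starting equally soon in both arms. Scheduled scans are timed from the end of radiotherapy (Section 8.4). With seven weeks of IMRT on schedule, the 9-month and 12-month scans fall near weeks 46 and 59 from IMRT start, each within one month. Weeks 51 and 52 lie between those windows, so a one-week shift would rarely reclassify a progression found on a scheduled scan.
- **The gap is probably short.** Section 3.1 requires screening labs within 14 days of treatment initiation and Section 8.1.1 places them before registration. Unless labs are repeated, the interval is about two weeks at most. PFS and survival curves with origins that close can still be read together with care.
- **A randomization clock may not remove the offset.** If first treatment, rather than IMRT, starts equally soon in both arms, Arm 2's IMRT begins a week later and the offset remains. It is then a consequence of the assigned schedule, not of the endpoint definition.
- **The evaluable-only analysis is a stated choice.** A reader might infer that the treatment-start clock is what drops untreated patients from the gate. The documents do not support that. The analysis set is fixed separately in Section 9, and moving the clock leaves it unchanged.

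The reply does not answer the core of the point: the endpoint that decides the trial has a post-randomization origin, its neighbors do not, and no rule covers the patient who never starts.

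**Conclusion.** The inconsistency is real and should be corrected, because it affects the metric that gates each arm and selects between them. Its expected numerical effect is small. The arm offset is worth at most about 0.5 to 0.6 points in Arm 2's favor at an underlying 60% to 70%, moving selection from 50% to about 52%. That holds only if IMRT starts equally soon in both arms and the lead-in week is event-free. Under a constant hazard it is near zero.

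A reader might infer that starting at treatment inflates 1-year PFS by one or two points for a gap of a few weeks. That does not follow: under a constant hazard the gap changes nothing, and with an event-free gap the sign reverses.

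The part that could change a decision is how randomized, untreated patients are counted, since one added failure at the threshold is enough. How often such patients will occur is not stated. The 10% allowance (5 of 45 per arm) covers drop-out and ineligibility of every kind and is only an upper guide.

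**What to change.** - Measure PFS, time to progression, overall survival and the 1-year landmarks from the date of randomization in both arms, and say that study entry means that date.
- Keep the planned evaluable set for the gate and for selection, and define evaluable for efficacy before outcome data are examined.
- Report 1-year PFS in all randomized patients as a sensitivity analysis, stating how a patient who never starts treatment is counted.

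Replacing the gate's analysis set with all randomized patients would be more than a wording change. It would alter a rule designed around 40 evaluable patients, which is why the all-randomized estimate belongs beside the gate and not in place of it.

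The cost is an edit to Sections 6.1.3 and 9 and a little more analysis work. The all-randomized estimate may be less favorable than the evaluable one. The sample size stays at 90.

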6.2 Methods of Measurement

Imaging based evaluation is preferred to evaluation by clinical examination. The same imaging modality must be used throughout the study to measure disease.

6.2.1 CT and MRI

CT and magnetic resonance imaging (MRI) are the best currently available and most reproducible methods for measuring target lesions. Conventional CT and MRI should be performed with contiguous cuts of 10 mm or less in slice thickness. Spiral CT should be performed by use of a 5 mm contiguous reconstruction algorithm. This specification applies to tumors of the chest, abdomen, and pelvis, while head and neck tumors, and those of the extremities require specific procedures.

6.2.2 Clinical Examination

Evaluation of measurable disease in the primary site as well as nodal sites by ENT examination should be recorded at baseline. Determination of complete response will occur through radiologic imaging as well as the post-protocol endoscopic examination.

6.2.3 Cytology and Histology

Cytologic and histologic techniques can be used to differentiate between complete and partial response in rare cases (e.g., after treatment to differentiate residual benign lesions and residual malignant lesions in germ cell tumors).

Cytologic confirmation of the neoplastic nature of any effusion that appears or worsens during treatment is required when the measurable tumor has met response or stable disease criteria.

Should primary site biopsy, primary site salvage, and/or neck dissection be conducted, the pathologic response will be recorded.

6.2.4 FDG-PET Scan

The ideal post-chemoradiotherapy response assessment method would accomplish two goals: 1) accurately detect viable residual disease amenable to surgical consolidation and 2) be prognostic for longer term clinical outcomes including PFS. Head and neck clinical examination alone has an accuracy of less than 50% for residual neck nodal disease,⁶³ while post-radiation diagnostic CT has higher sensitivity than clinical exam but unsatisfactory specificity.^{64,65} An increasing body of literature suggests that post-chemoradiotherapy positron emission tomography (PET), performed 8-12 weeks following completion of radiotherapy has improved accuracy relative to CT for classification of complete response in PULA HNSCC. The negative predictive value (NPV) for determination of residual neck disease, in particular, ranges from 92-100%.⁶⁶⁻⁶⁹ The University of Pittsburgh institutional experience indicates that serial PET/CT scans permit safe deferral of planned neck dissection following chemoradiotherapy. Moreover, a PET scan added to a diagnostic contrasted CT is superior to clinical examination or diagnostic CT alone

(utilizing RECIST criteria 1.0) with regard to correlation with PFS.⁷⁰ However, RECIST 1.0 criteria were developed primarily for response assessment in the metastatic solid tumor setting, where patients are treated with palliative systemic therapy. RECIST 1.0 criteria inadequately address the post-chemoradiotherapy setting. Specifically, a CR in accordance with RECIST 1.0 requires disappearance of all target lesions, including pathologic lymph nodes. However, non-pathologic, subcentimeter lymphadenopathy can persist after chemoradiotherapy. RECIST 1.1 now incorporates new guidelines for the measurement of nodal disease, and for determination of CR, a short axis of < 1 cm is no longer considered residual disease. The accuracy of the RECIST 1.1 criteria for assessment of residual disease or as a predictor of PFS following chemoradiotherapy for PULA HNSCC is not reported.

To date, the majority of PET/CT literature conducted has been retrospective. The sole prospective study of PET/CT versus CT for first response assessment following chemoradiotherapy was performed at MDACC.⁶⁶ This study found that PET/CT was not superior to diagnostic CT alone for the accuracy of response assessment in unselected PULA HNSCC patients. However, in high risk patients defined as HPV-negative, non- oropharynx, and/or tobacco-exposed, PET/CT outperformed CT. The study has been criticized for lack of integration of a diagnostic contrasted CT into the PET/CT acquisition algorithm, although PET/CT results were interpreted with knowledge of a separate contrasted diagnostic CT; such integration enhances per-lesion sensitivity and specificity in head and neck cancer staging⁷¹ and is of theoretical utility in the post-treatment patient. The CT criteria used in the MDACC study to classify nodal disease were clinical and related to RECIST. However, long axis nodal measurements were utilized with the following categorization:

- Pathologic (residual disease) nodes: > 15 mm in longest diameter and/or necrotic appearance.
- Indeterminate nodes: 10-15 mm in longest diameter and non-specific CT findings.
- Non-pathologic nodes: < 10 mm in longest diameter and non-necrotic (CR).

At the University of Pittsburgh, the standard of care following definitive chemoradiotherapy for PULA HNSCC has been integrated PET/CT. Following PET/CT patients are placed into four clinical categories: Negative PET/CT (Complete Response); Probably Negative PET/CT (Low clinical concern; follow up indicated); Probably Positive PET/CT (Clinical concern; tissue sampling indicated); Positive PET/CT (Definite residual disease). This categorization has been found to correlate with clinical outcomes, specifically PFS.⁷²

Definition of CR following chemoradiotherapy therefore has two relevant, literature-based definitions which may be of clinical utility: 1) Quantitative anatomic criteria (RECIST 1.1); 2) Integrated PET/CT criteria.

Complete Response: Modified RECIST 1.1 (see section 6.1)

- Disappearance of primary tumor. Irregular contour of the tumor bed is consistent with -radiation change.
- Decrease in measurable pathologic neck lymph nodes to short axis measurement < 10 mm and non-necrotic appearance with normalization of nodal configuration. Increased enhancement may be attributable to radiation change.
- No new pathologic lesions.

7. DRUG INFORMATION

7.1 Pembrolizumab

7.1.1 Study Drug Materials

Pembrolizumab drug substance is produced at two locations to yield: 1) a partially formulated aqueous solution stored under refrigerated conditions (2-8°C) at a concentration of 40-50 mg/mL in 10 mM histidine buffer, pH 5.2-6.8, and 2) a fully formulated aqueous solution stored frozen (-40°C) at a concentration of 22.5-27.5 mg/mL in 10 mM histidine buffer, pH 5.2-5.8 containing 7% sucrose and 0.02% polysorbate 80. The drug products are sterile filtered into Type I glass vials intended for single use.

Two drug product dosage forms are available for pembrolizumab: 1) a white to off-white lyophilized powder, 50 mg/vial, and 2) a liquid, 100 mg/vial.

- Pembrolizumab Powder for Solution for Infusion, 50 mg/vial (manufactured using the partially formulated drug substance), is reconstituted with sterile water for injection prior to use. It is formulated with L-histidine as buffering agent, polysorbate 80 (surfactant), sucrose as stabilizer/tonicity modifier, and hydrochloric acid (HCl) and/or sodium hydroxide (NaOH) for pH adjustment (if necessary).
- Pembrolizumab Solution for Infusion, 100 mg/vial is a liquid drug product (manufactured using the fully formulated drug substance), and has the identical formulation as that of the reconstituted lyophilized vial.

The product after reconstitution with sterile water and the liquid drug product are a clear to opalescent solution which may contain proteinaceous and extraneous particulates.

Both the pembrolizumab reconstituted product and the liquid product are intended for IV administration and both can be further diluted with normal saline in IV containers made of polyvinyl chloride (PVC) or non-PVC material.

7.1.2 Pembrolizumab Study Drug Storage

Both pembrolizumab drug product dosage forms are to be stored under refrigerated conditions (2° C– 8° C) and in a secure location.

Note: No other use of pembrolizumab study drug intended for use in this trial is authorized by the sponsor. The investigator (or designee) will be responsible for the appropriate handling and disposition of residual study drug in partially used vials.

Vial Labels: Pembrolizumab vial labels will bear the appropriate label text for investigational agents, as required by governing regulatory agencies.

Complete study drug information (including packaging, labeling, storage and disposition) is provided in the Pembrolizumab Investigator's Brochure (IB).

7.2 Cisplatin

Refer to the package insert for additional information.

Formulation: Each vial contains 10 mg of DDP, 19 mg of sodium chloride, 100 mg of mannitol, and hydrochloric acid for pH adjustment. One vial is reconstituted with 10 ml of sterile water. The pH range will be 3.5 to 4.5. Cisplatin injection also is available from the manufacturer in aqueous solution, each ml containing 1 mg cisplatin and 9 mg NaCl and HCl or NaOH to adjust pH.

Mechanism of Action: The dominant mode of action of cisplatin appears to be inhibition of the incorporation of DNA precursors, although protein and RNA synthesis are also inhibited. Although this drug seems to act as an alkylating agent, there are data to indicate that its mode and sites of action are different from those of nitrogen mustard and the standard alkylating agents.

Administration: Cisplatin will be given as a bolus, infused over 1-2 hours along with appropriate hydration and anti-emetics.

Storage and Stability: Reconstituted solution of cisplatin is stable for 20 hours when stored at 27° C and should be protected from light if not used within 6 hours. The vials and injection should not be refrigerated. Cisplatin has been shown to react with aluminum needles, producing a black precipitate within 30 minutes.

Adverse Events: Human toxicity includes nausea, vomiting, renal toxicity (with an elevation of BUN and creatinine and impairment of endogenous creatinine clearance, as well as renal tubular damage, which appears to be transient), ototoxicity (with hearing loss that initially is in the high-frequency range, as well as tinnitus), and hyperuricemia. Much more severe and prolonged toxicity has been observed in patients with

abnormal or obstructed urinary excretory tracts. Myelosuppression, often with delayed erythrosuppression, is expected.

Supply: Cisplatin is commercially available. The use of drug(s) or combination of drugs in this protocol meets the criteria described under Title 21 CFR 312.2(b) for IND exemption.

